Clinic Social Network: This is a 4-question survey used to provide information about how people interact in each clinic. The survey will include a staff list in order to identify co-workers that regularly interact. Once data has been collected, names from the staff list will be deleted.

Knowledge of Evidence-Based Smoking Cessation Treatment: This is a 16-item scale developed by our team to assess knowledge of evidence-based smoking cessation treatment (e.g. that most people with SMI want to quit and that varenicline is safe and effective for people with SMI).

Self-Efficacy: Assessing self-efficacy to deliver evidence-based smoking cessation treatment measured as a numeric score created by averaging 10 items adapted from Compeau & Higgins' task-focused self-efficacy scale⁴³ (score>8 = high self-efficacy).

Motivation Measures: Measured by assessing the degree to which providers agree or disagree with each statement, and the degree to which providers find each item important or not important. Statements deal with aspects of the IMPACT intervention to improve use of evidence-based smoking cessation treatment.

Beliefs about Motivational Interviewing Questionnaire: A 7-question survey assessing the extent to which each person agrees with statements about motivational interviewing.

Importance and Confidence of Using Motivational Interviewing: A 6-question survey assessing the importance and confidence each person has with motivational interviewing.

Perceived Usefulness of Motivational Interviewing Avatar: A 6-item survey assessing the impact of the avatar on each person's use of motivational interviewing and performance in the study.

Fidelity Measures

Avatar Motivational Interviewing Performance Measurements: Providers will conduct 15-minute practice conversations where they practice use of motivational interviewing techniques in simulated conversations about tobacco smoking cessation with patient avatars. An online dashboard will give providers an individualized report on their performance each time they practice.

Fidelity to Motivational Interviewing: Standardized Actor Interviews: Providers will conduct 30-minute audio-recorded phone interviews with standardized patient actors. These standardized patient actors are trained actors playing roles of patients with SMI who smoke. Used to assess fidelity to motivational interviewing.

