Fidelity to behavioral smoking cessation counseling: Standardized Actor Interviews: Providers will conduct 30-minute audio-recorded phone interviews with standardized patient actors. These standardized patient actors are trained actors playing consumers with SMI who smoke. Used to assess fidelity to smoking cessation behavioral counseling sessions.

Smoking and Smoking Cessation Processes of Care, Patient Measures

Providers will document smoking-related processes of care during the study (see IMPACT Study Medical Record Variables document). We will work with each community mental health clinic on how providers will do this. At Johns Hopkins, this information will be entered into EPIC using smart forms and adapting current clinic note templates. For other study clinic sites, data will come from a combination of electronic health records and from REDCap surveys that clinic provider participants complete when they assess smoking status or provide smoking cessation treatment. If the other sites are not able to change their electronic health records to collect smoking cessation processes of care or provide documentation of smoking cessation processes of care directly to us, we plan to use REDCap to supplement available electronic health record data. We describe in more detail below in the data management section.

[figure not shown]
Data Management:

Qualitative data. Interview data will be audio or video-recorded and recordings will be transcribed using Production Transcripts, Inc or another approved Johns Hopkins vendor. Names will be removed from transcripts. Recordings will be stored in a Johns Hopkins secure network drive and will be destroyed when analyses are complete. Standardized actor interview recordings will be reviewed by experts in motivational interviewing and smoking cessation behavioral counseling to assess for fidelity to motivational interviewing

practices and fidelity to IMPACT smoking cessation behavioral counseling sessions. These recordings will be stored in a Johns Hopkins secure network drive or OneDrive.

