Quantitative data. Each participant will be assigned a unique study ID number for data collection. Study team members are trained to protect integrity and confidentiality of the data. Staff and provider questionnaire data will be stored in a Johns Hopkins REDCap database. Kognito, a health simulation company, developed the avatar simulations for this project and hosts the avatar training platform and dashboard. Avatar performance measurement data for motivational interviewing practice conversations is accessible only by the individual study participant (provider) and the study team, not shared outside Kognito. Kognito stores data securely behind two firewalls.

Figure. Data sources, management and security.

This figure describes planned data management and security for this study. We developed this plan with [name], IT Director for the Johns Hopkins ICTR. The ICTR/CCDA will serve as an honest broker both for data coming from Johns Hopkins and from non-Johns Hopkins clinic sites. They will create limited datasets for

patient data for study team use on a study team SAFE Desktop including linking REDCap process of care data from to the appropriate patient. REDCap: We will store questionnaire data from staff/providers who agree to participate in the study in a Johns Hopkins REDCap database, restricted by study site. REDCap will also be used if needed for providers at non-Johns Hopkins study sites to document processes of care information for smoking cessation treatment to supplement data from electronic health records. One site (Vesta) plans to use a spreadsheet to document deidentified process of care data to be placed on a Johns Hopkins OneDrive. EPIC: Johns Hopkins EPIC data from smartforms developed for this project and from clinic notes will be used for process of care information at the Johns Hopkins site. Additional data from EPIC will be used including for demographics, medications, and information about number of outpatient encounters. (see IMPACT Study Medical Record Variables document). Weekly reports of process of care data will be provided to the study team, not identifying patients. SFTP: Electronic medical record data from non-Johns Hopkins study sites will be transmitted to Johns Hopkins through SFTP. The ICTR/CCDA will serve as an honest broker and store data on a CCDA Safe Desktop while preparing the limited datasets for the study team.

- c. Blinding, including justification for blinding or not blinding the trial, if applicable.

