Not applicable

Justification of why participants will not receive routine care or will have current therapy stopped.
Not applicable

- d. Justification for inclusion of a placebo or non-treatment group
Not applicable
- e. Definition of treatment failure or participant removal criteria.
Not applicable
- f. Description of what happens to participants receiving therapy when study ends or if a participant's participation in the study ends prematurely.
Not applicable

5. Inclusion/Exclusion Criteria

Community mental health clinic staff (e.g., licensed counselor, psychologist, social worker, nurse practitioner, physician, organizational leader, clinic director, administrative assistant) at one of the 4 community mental health clinic study sites. All are 18 years and older and English-speaking.

Clinic patients are by definition persons with serious mental illness seeking treatment at community mental health outpatient clinics. All are 18 years and older.

6. Drugs/ Substances/ Devices – Not applicable

- a. The rationale for choosing the drug and dose or for choosing the device to be used.
- b. Justification and safety information if FDA approved drugs will be administered for non-FDA approved indications or if doses or routes of administration or participant populations are changed.
- c. Justification and safety information if non-FDA approved drugs without an IND will be administered.

7. Study Statistics

- a. Primary outcome variable and analytic plans.

We will conduct three main analyses. First, we will assess the effects of the implementation intervention (baseline and 12 months) on providers' knowledge and self-efficacy, the mechanisms through which the

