To analyze the standardized actor interviews, we will use the Motivational Interviewing Treatment Integrity (MITI) rating system and our IMPACT Smoking Cessation Counseling Session skills Assessment Form. For MITI: We will MITI code random 30-minute segments of audio-recorded interactions with standardized patient actors. Standardized consumer scenarios will be scripted to reflect the kind of situations community mental health clinicians would likely encounter with clients; this method has predictive validity in terms of providers' performance with real patients.⁴⁴ "Global" scores provide benchmarks of "fair" or "good" on the technical (e.g. capacity to elicit motivations for change) and relational (person-centered) aspects of motivational interviewing. "Behavior Counts" are tallies of 10 specific clinician behaviors, e.g. giving information and "persuading with permission." Summary measures indicate the degree to which clinicians are motivational interviewing adherent (e.g. affirm, emphasize autonomy, seek collaboration), motivational interviewing non-adherent (e.g., confront, persuade), and show an appropriate ratio of questions to reflections. For fidelity to evidence-based smoking cessation treatment: all interviews will be scored by our team to assess individual clinician's skills implementing the intervention.

- b. Secondary outcome variables. N/A
- c. Statistical plan including sample size justification and interim data analysis. N/A
- d. Early stopping rules. N/A

8. Risks

Risk of loss of confidentiality and negative implications for employment are the main risks. We expect these risks to be extremely low. Plans to minimize this risk are described below.

- a. Medical risks, listing all procedures, their major and minor risks and expected frequency.

For the implementation intervention, community mental health clinic providers (including primary care providers) are already providing care including some smoking cessation treatment for their patients with serious mental illness. For this project, we will work with community mental health clinic providers to implement evidence-based best tobacco smoking cessation practices. The evidence-based practices in this project are based on current guidelines and are within the clinicians' current scope of practice. Thus, we do not expect there to be an increased risk for clinic patients.

Community mental health clinic providers and staff may become tired or bored during surveys or interviews.

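### The plan does not say whether raters of the standardized-actor recordings are masked to wave, site and provider, or in what order they score them

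*Combined protocol and SAP*

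**What the plan says.** Table 2 schedules standardized-actor interviews for all providers, about 25 per site, at 3, 6 and 12 months. There is no baseline wave. The recordings serve two fidelity measures, one for motivational interviewing and one for cessation counseling.

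On who rates them:
- Section 4, Data Management (Qualitative data): "Standardized actor interview recordings will be reviewed by experts", whose fields are given as motivational interviewing and cessation counseling.
- Section 7a, motivational interviewing: "We will MITI code random 30-minute segments of audio-recorded interactions with standardized patient actors".
- Section 7a, counseling skills: "all interviews will be scored by our team to assess individual clinician's skills implementing the intervention".

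The first statement alone leaves open whether the experts are independent. The two in 7a place the scoring with the study team. Under Training and Expert consultation in Section 4, study team members also deliver the trainings and advise prescribers and therapists throughout the 12 months.

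On masking, the only text is item 4c. Its prompt reads "Blinding, including justification for blinding or not blinding the trial, if applicable" and its answer is "Not applicable". Data Management removes names from transcripts but describes no similar step for the actor recordings. No section mentions coded files, scoring order, separation of raters from trainers, double coding or a check of rater agreement.

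**The concern.** MITI global scores and a skills form made by the study team both rest on judgement, so the rater's expectations can move them. A rater who knows that a file comes from month 12, or from a provider the rater has trained, may expect a better performance. If files are scored as they arrive, any change in the rater's own standard over the year falls on the same axis as time since training.

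In a trial with a concurrent control arm, drift shared by both arms would largely cancel. This study has no such arm, so drift would look like a change in provider skill. Raters who know the site could shift site contrasts in the same way. The results are meant to inform a large-scale trial (end of Section 1), and a skill trajectory produced partly by the raters would be a poor guide to its design.

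**Working it through.** The plan has no figure to reproduce. Item 7c, on the statistical plan and sample size, is answered N/A, and no alpha, SD or effect size is given for these scores. The check has three steps.

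**1. Does anything in the plan already protect the ratings?** Section 7a codes a random 30-minute segment. Section 4, Fidelity Measures, says: "Providers will conduct 30-minute audio-recorded phone interviews with standardized patient actors". The segment is as long as the interview, so drawing it at random hides nothing about wave, site or provider.

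**2. How many files are involved?** Section 4 (Overview and Study sites) plans five clinics; the Surveys paragraph, Section 5 and Section 7a refer to four. With about 25 providers per site and three waves:
- four sites: 25 × 4 = 100 providers, 100 × 3 = 300 recordings
- five sites: 25 × 5 = 125 providers, 125 × 3 = 375 recordings

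This assumes one interview per provider per wave serves both instruments, and that every provider completes every wave. Section 4 also estimates 120 employee participants in total, including non-providers, so 125 is an upper bound that the plan's own total does not reach.

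**3. How much would a rater shift matter if waves were compared?** This is an illustration and not a planned test. Assumptions: paired comparison of month 12 with month 3, no true change, two-sided alpha 0.05, within-provider correlation ρ, rater shift of b SD between waves, normal approximation, clustering by site and rater ignored.

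SE of the mean change in SD units = √(2(1 − ρ)/n)

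P(nominal significance) = Φ(b/SE − 1.96) + Φ(−b/SE − 1.96)

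With ρ = 0.5:

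| Completers n | SE | b = 0.1 | b = 0.2 | b = 0.3 |
|---|---|---|---|---|
| 50 | √(1/50) = 0.141 | 11% | 29% | 56% |
| 75 | √(1/75) = 0.115 | 14% | 41% | 74% |
| 100 | √(1/100) = 0.100 | 17% | 52% | 85% |
| 125 | √(1/125) = 0.089 | 20% | 61% | 92% |

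For example, n = 100 and b = 0.2 give b/SE = 2.00, so P = Φ(0.04) + Φ(−3.96) = 0.516.

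For b = 0.2 over ρ from 0.3 to 0.7 and n from 50 to 125, the result runs from 22% (n = 50, ρ = 0.3) to 82% (n = 125, ρ = 0.7). With b = 0 it is 5%.

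**The case against.** The strongest reply is that no planned analysis is exposed. The three main analyses in 7a concern provider knowledge and self-efficacy, consumer-level care and abstinence, and mediators and moderators. None uses actor-interview scores. For those scores 7a describes benchmarks, behavior counts and summary measures, with no test between waves or sites. Without a baseline wave they cannot give a pre/post effect. Table 2 reserves the label of primary fidelity measure for the documented processes of care, and the study is a pilot. All of this stands, and it limits the point to descriptive contrasts on a supporting measure.

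The reply also rightly resists two inferences that a reader might draw:
- **That 4c declares the raters unmasked.** The prompt asks about blinding the trial. With no comparison arm, the answer given is a proper one, and it says nothing about raters.
- **That raters do know wave and site, score in calendar order, or rate providers they have trained.** No section says so. Overlap between raters and trainers or consultants is plausible because both belong to the study team, but it is not stated.

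Finally, the percentages show what a shift would do if it occurred, not that one is likely, and the larger values of n assume almost no attrition. That too is correct, which is why smaller n and other correlations are shown.

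The reply does not supply a safeguard. Repeating the ratings at three waves invites comparison over time, formal or not, and bias distorts a descriptive contrast as much as a tested one.

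**Conclusion.** The point holds as an unaddressed and avoidable risk of bias. The study team makes subjective ratings at three waves, the same team trains and advises the providers, and the plan describes no masking and no scoring order. Expectation or drift could distort descriptive wave and site contrasts in standardized-actor fidelity.

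The size is conditional. Under the stated assumptions a 0.2 SD rater shift would make a 12- versus 3-month comparison nominally significant about 29% of the time with 50 completers, 52% with 100 and 61% with 125, against a nominal 5%. The shift, correlation, alpha and number of completers are all assumed.

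A reader might go further and infer that the trial's main findings are biased. The documents do not support that, because these scores do not enter the main analyses or the primary process-of-care fidelity measures. The change is worth making because it is cheap, not because a result is known to be wrong.

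**What to change.** - Give each recording a random code that hides wave, site and provider identity, with the key held by someone who does not rate. The plan already assigns study IDs, so this is a small extension.
- Score in random order, in batches that mix waves and sites, or all together after the 12-month interviews. Mixing waves means holding back some earlier files until later ones are in.
- Where feasible, use raters who did not train, coach or consult with the provider concerned. Spread each site's files across raters, because otherwise this rule could tie raters to sites and create the site bias it is meant to prevent.
- State these steps in 7a. If masking is not feasible for some files, say so and describe the wave and site contrasts as unmasked.

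The cost is relabelling about 300 to 375 files and keeping a randomized scoring list, both by existing staff, with scoring batched or delayed. Voices and content may still reveal the provider or the wave, so the bias is reduced and not eliminated. Masking does not measure rater agreement either; a double-coded subset would do that, but it is a separate choice.

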The study will result in a set of training and implementation tools and resources for community mental health clinics to address tobacco smoking. Results also will inform the future design of a large-scale trial testing strategies to increase delivery of evidence-based smoking cessation treatment for SMI in community mental health settings.

2. Objectives

The specific aims are:

Aim 1: To inform implementation intervention development, examine barriers to evidence-based smoking cessation treatment in community mental health clinics serving consumers with SMI.

1. What do providers in a community mental health organization perceive as the key barriers to delivery of evidence-based smoking cessation treatment, and what strategies could help to overcome these barriers?

Aim 2: Assess the implementation intervention's effects on providers' knowledge, self-efficacy, and delivery of evidence-based smoking cessation treatment and preliminary measures of consumers' abstinence from tobacco smoking. The intervention will:

1. Increase providers' knowledge of smoking cessation treatment for consumers with SMI.
2. Increase providers' self-efficacy to deliver evidence-based smoking cessation treatment.
3. Increase providers' delivery of the four key components of evidence-based smoking cessation treatment: assessment of smoking status & willingness-to-quit, pharmacotherapy prescribing, and behavioral counseling.
4. Increase abstinence from tobacco smoking among consumers with SMI.

Aim 3: Assess the acceptability, appropriateness, and feasibility of the implementation intervention to increase delivery of evidence-based smoking cessation treatment:

1. The implementation intervention will be perceived as acceptable, appropriate, and feasible by community mental health clinic providers.

3. **Background** (briefly describe pre-clinical and clinical data, current experience with procedures, drug or device, and any other relevant information to justify the research)

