Few mental health providers deliver evidence-based smoking cessation treatment and many mental health clinics lack standard systems for screening, monitoring, and treating tobacco smoking.^{12,22} Community mental health settings are often under-resourced and providers face multiple competing demands and smoking cessation has not historically been an organizational priority. As noted above, mental health providers may face knowledge and self-efficacy barriers that impede their delivery of evidence-based smoking cessation treatment.^{12,20-23} Nonetheless, mental health providers' extensive experience working with consumers with SMI makes them optimally positioned to deliver effective cessation treatment for tobacco smoking, the leading cause of premature mortality among people with SMI.

4. Study Procedures

- a. Study design, including the sequence and timing of study procedures (distinguish research procedures from those that are part of routine care).
- b. Study duration and number of study visits required of research participants.

Currently this protocol is being submitted as a study where all study procedures are delivered remotely. If and when COVID-19 restrictions are lifted, we may submit a petition to have some of the study activities in-person as appropriate.

Overview: We will work with 5 community mental health clinics in Maryland. This project's goal is to implement evidenced-based tobacco smoking cessation treatment in community mental health clinics serving the population of persons with serious mental illness. Tobacco smoking cessation treatment involves behavioral counseling and pharmacotherapy. The main outcome of the project is the utilization of 4 evidence-based practices in the clinic setting: 1) screening for tobacco use in all patients, 2) an assessment of willingness to quit for those who smoke, 3) referral and utilization of behavioral counseling for those interested in cutting down or quitting smoking, 4) receipt of pharmacotherapy for those interested in cutting down or quitting smoking. The community mental health clinics are already providing some treatment for smoking cessation for their patients. The evidence-based practices in this project are within their scope of practice. The implementation intervention is 12 months.

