Fidelity to Motivational Interviewing: Standardized Actor Interviews will be conducted to assess fidelity to motivational interviewing.	All providers (~25 per site)	30 minutes		3, 6, 12 months
Fidelity to behavioral smoking cessation counseling: Standardized Actor Interviews will be conducted to assess fidelity to smoking cessation behavioral counseling sessions				
Smoking and Smoking-Cessation Measures				
These are our primary measures of fidelity to evidence-based smoking cessation treatment.	All mental health consumers (patients) (~3000 per site)			Baseline through 12 months
Guideline-concordant smoking cessation treatment: Measures will be calculated at site & provider levels				
Smoking status assessment rates: % of visits where smoking status assessment is documented.				
Willingness-to-quit assessment rates: % of visits where willingness-to-quit assessment is documented.				
Prescription Rates: % of willing-to-quit smokers prescribed, or offered but refused, cessation pharmacotherapy. ²				
Behavioral Counseling Rates: (1) % of not willing-to-quit				

smokers given brief behavioral counseling to increase willingness-to-quit; and (2) % of willing-to-quit smokers who were referred to the clinic's cessation counselor. ² Among willing-to-quit smokers referred the counselor, we will also measure the number of counseling sessions completed.			
7-day abstinence: % of willing-to-quit consumers abstinent for ≥ 7 days self-report, documented in the EMR	All mental health consumers (patients) (~3000 per site)		Baseline through 12 months
Other Patient Measures Year of birth, gender, race/ethnicity, primary mental health diagnosis, hospitalization during the study period	All mental health consumers (patients) (~3000 per site)		Baseline through 12 months

Qualitative Data Collection

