implementation intervention is designed to improve delivery of evidence-based smoking cessation treatment, using a generalized linear mixed effects modeling approach. The mean model will include a binary pre/post indicator, fixed effects for the four study sites, and provider demographic characteristics. Second, we will evaluate the effects of the implementation intervention (baseline and 12 months) on consumer level guideline-concordant care and 7-day smoking abstinence outcomes using a multi-level modeling approach. Third, we will assess mediators and moderators. Specifically, we will test whether providers' knowledge and self-efficacy mediated the implementation intervention's effects on consumer outcomes by estimating the magnitude of attenuation on intervention effects in the multi-level models of consumer outcomes with versus without these potential mediators. We will also assess the potential moderating effects of implementation climate by adding appropriate interaction terms to main models. We will use descriptive statistics to analyze survey measures of staff perceptions of the acceptability, feasibility and appropriateness of the implementation intervention strategies and the IMPACT evidence-based practices. Interview transcripts will be analyzed in NVivo V.11, using inductive coding to identify key themes. Survey analysis will be done using Stata 14 or SAS software.

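### The baseline-versus-12-month contrast for 7-day abstinence cannot isolate an intervention effect, because the denominator comes from an assessment given only to current smokers

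*Combined protocol and SAP*

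**What the plan says.** Aim 2, item 4 (Section 2) states the hypothesis: "Increase abstinence from tobacco smoking among consumers with SMI".

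Table 2 (Section 4) defines the outcome as the percentage "of willing-to-quit consumers abstinent for ≥ 7 days self-report, documented in the EMR". The Section 4 Overview describes the step that creates this group: "an assessment of willingness to quit for those who smoke". The prescribing measure in the same table names the class more directly, as the percentage "of willing-to-quit smokers prescribed, or offered but refused, cessation pharmacotherapy".

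Section 7a sets the contrast: "Second, we will evaluate the effects of the implementation intervention (baseline and 12 months"), and applies it "on consumer level guideline-concordant care and 7-day smoking abstinence outcomes using a multi-level modeling approach". A later step in Section 7a asks whether provider knowledge and self-efficacy mediate the effect on consumer outcomes, judged by how far the effect shrinks when they enter the model.

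The item "Justification for inclusion of a placebo or non-treatment group" in Section 4 is answered as not applicable, and the Overview says that the clinics already give some cessation treatment.

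The protocol does not state when a person is classed as willing to quit, whether the 12-month group is the same people as the baseline group, or what period counts as baseline.

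**The concern.** A before/after contrast is informative only if the outcome could have taken its 12-month value at baseline without the intervention. Screening, prescribing and counseling rates meet that condition: each can take any value before launch and can rise or fall. Abstinence in this group does not. Someone just recorded as a smoker willing to quit can hardly also be recorded as abstinent for at least 7 days. A year later the same person has had a year in which to quit, with or without the study. The two time points differ in time at risk, so the baseline figure does not show what would have happened without the intervention.

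Three things are at stake. Aim 2 item 4 could be reported as met on background quitting alone. The same quitting would enter the mediation step: provider scores are expected to rise over the same interval, so it could be apportioned to them as a mediated effect. And Section 1 says that the results will inform a large-scale trial, which an inflated effect would mislead.

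**Working it through.** The plan gives no baseline abstinence rate, background quit rate, significance level or sample size, so there is no figure to reproduce. The check takes the possible readings of the denominator in turn and then sizes the first.

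**Readings of the denominator**

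| Reading | Baseline value | 12-month value | What the contrast shows |
|---|---|---|---|
| Fixed at baseline, or everyone ever classed as willing | Near 0 | Background quitting q plus any true effect d | q + d, all reported as effect |
| Re-formed from current smokers at each time point | Near 0 | Near 0 | Nothing |
| Baseline is an earlier period of equal length among people classed as willing before it | Background quitting | Background quitting plus d | d, if there is no time trend |

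Only the third reading gives a usable contrast, and the protocol describes no such period.

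**Size of the bias under the first reading**

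Estimated change = (q + d) − 0. With d = 0 it equals q. For assumed q of 1%, 3% and 5%, it is +1, +3 and +5 percentage points, whatever the sample size.

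**Number of people: an upper limit**

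Inputs: about 3,000 patients per site (Table 2); five sites (Section 4); 53% smoking and 65–80% of smokers wanting to quit (Section 3).

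- 5 × 3,000 × 0.53 × 0.65 = 5,167.5, about 5,168
- 5 × 3,000 × 0.53 × 0.80 = 6,360
- With four sites, as the Surveys text, Section 5 and Section 7a have it: 4,134 to 5,088

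With five sites and no intervention effect, the number abstinent at 12 months, against about 0 at baseline, would be:

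- q = 1%: 52 to 64
- q = 3%: 155 to 191
- q = 5%: 258 to 318

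These totals assume that every patient is assessed and documented and that the literature rates apply, so they are a ceiling.

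**Would the false effect be significant?**

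Take a paired exact (McNemar) test with 0 losses and k gains. The two-sided p is 2 × 0.5^k: 0.0625 for k = 5 and 0.031 for k = 6. At an assumed 5% level, a false positive needs at least 6 quitters. The chance is P(X ≥ 6) with X binomial(n, q):

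| People with data | q = 1% | q = 3% | q = 5% |
|---|---|---|---|
| 100 | 0.1% | 8% | 38% |
| 200 | 1.6% | 56% | 94% |
| 517 (10% of 5,168) | 41% | 99.8% | >99.9% |
| 1,000 | 93% | >99.9% | >99.9% |

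As a cross-check, Fisher's exact test for 5 of 517 against 0 of 517 gives p = 0.062, and for 6 of 636 against 0 of 636 gives p = 0.031. Both tests ignore clinic clustering and neither is the planned multi-level model, so they illustrate the point and do not predict the result.

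**The case against.** A reader might infer more: that baseline abstinence is zero by definition and that Aim 2 item 4 cannot fail. The documents do not support that.

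- The classification date and the cohort rule are not stated, and Table 2 lists collection as running from baseline through 12 months, not as two snapshots. If the group is re-formed from current smokers, the aim could hardly succeed. Table 2 also says consumers here and smokers in the companion measures, though that is weak evidence, because the class still comes from the smokers-only assessment.
- Section 4 refers to a separate medical record variables document that may hold the definition and is not available here.
- A false positive is not assured. Section 4 allows for sites that cannot adapt their records, and Section 3 notes that clinics may lack systems for tracking smoking status, so documented numbers may be far below the ceiling. With 10% of the ceiling and 1% quitting, the result is borderline.

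It can also be said that this is a pilot, that Section 2 already calls the abstinence measures preliminary, that Section 4 names four care practices as the main outcome, and that lack of a comparator is the ordinary limit of an uncontrolled design.

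The first three points stand and set the limits of the claim. The pilot argument stands in part: it lowers the stakes, but Section 7a still plans an effect estimate and a mediation analysis. The last point misses what is particular to abstinence. The care-process measures share the lack of a comparator, but none starts near zero because of how its denominator is formed.

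**Conclusion.** The concern holds in a limited form. The planned contrast misleads under the fixed or ever-willing reading and is empty under the re-formed reading. The reading that would make it work needs an equal-length period before implementation, which the protocol does not describe. This is therefore more than a missing definition.

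Under the first reading the bias is the whole background quit rate: +1 to +5 percentage points if that rate is 1% to 5%, which is an assumption. Statistical significance depends on the number of documented people, with 5,168–6,360 as the ceiling. The conclusion rests on two inferences: that willing-to-quit consumers are those identified by the smokers-only assessment, and that the baseline value is taken at or near that assessment. It applies to abstinence only, and not in this form to the care-process measures. The change should be made, but the main outcome does not depend on it.

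**What to change.** 1. Remove 7-day abstinence from the baseline-versus-12-month effect model and from the mediation step in Section 7a. Keep both for the guideline-concordant care measures.
2. Define the cohort: consumers first recorded as smokers willing to quit, with that date as time zero. State the follow-up each person has and how many have no later status on record.
3. Report the proportion abstinent by 12 months with an interval that allows for clinic clustering, as a preliminary estimate with no effect claim. With four or five clinics that interval will be imprecise, so show the clinic-specific proportions too.
4. Optionally, add an equal-time look-back cohort, only at sites whose pre-launch records already hold smoking status in comparable form. Two cautions apply. Table 2 collects patient data only from baseline onward, and some sites may rely on REDCap forms or a spreadsheet made for the study, so this would be an added extract. And the intervention itself changes how fully smoking status is documented, so the two cohorts may differ in ascertainment.

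The first three items cost wording in Section 7a and Table 2 and no new data collection. The price is that Aim 2 item 4 gives a descriptive estimate and not a test of increase, and its wording should be changed to match.
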